### 3.3. Missing or Incorrect Data

Discontinuation from study intervention is different from discontinuation from the study, and remaining study procedures will be completed as indicated by the study protocol unless the subject withdraws consent for participation in the study. The date of vital status for all patients who early term will be capped at 37 days post the early termination date. For all patients who complete the study through 9 months, the 10-month follow-up safety visit date will be capped at 307 days post study drug Day 1.

All data pertaining to the primary and secondary endpoints collected at any point during the study, both during study drug treatment and post-study drug treatment discontinuation, will be used for the primary analysis of the endpoints and its individual components.

### 3.4. Statistical Analyses

#### 3.4.1. General Considerations

Data summaries for categorical variables such as serious adverse events (SAEs) and adverse events of special interest (AESI) will use descriptive statistics including incidence for subjects with, as well as counts for number of events. Data summaries for continuous variables such as laboratory parameters will use descriptive statistics for mean, standard deviation, median, first and third quartiles, minimum, and maximum. Change from baseline will be calculated, with the addition of a 95% confidence interval. Within-group and between group changes from baseline for continuous parameters will be assessed.

#### 3.4.2. Baseline Characteristics

Descriptive statistics will be generated for demographic and pretreatment variables for the safety population defined in the protocol.

Medical history terms will be summarized by treatment group in the safety population. This will include:

- Congestive heart failure, defined as systolic or diastolic dysfunction, heart failure with reduced ejection fraction, or heart failure with preserved ejection fraction
- Diabetes, defined as type I or type II
- Atherosclerotic cardiovascular disease, defined as coronary artery disease, angioplasty, stent, myocardial infarction, cerebrovascular accident, or transient ischemic attack
- Hypertension
- Peripheral vascular disease defined as amputation or artery revascularization, stent, or angioplasty
- Dyslipidemia
- Anemia

- Secondary Hyperparathyroidism
- COVID-19 infection

#### 3.4.3. Protocol Deviations

Important protocol deviations will be summarized for the full analysis population. For the purposes of this protocol, important deviations are defined as any subject who:

- Entered the study even though they did not satisfy entry criteria
- Received wrong treatment or incorrect dose (i.e., patient not stopping IP when protocol required, patient not decreasing IP when serum phosphorus and iron indices indicate)
- Received excluded concomitant treatment, including commercial Auryxia
- Does not discontinue prescribed phosphate-lowering therapy or oral/IV iron therapy in response to low phosphorus or elevated iron indices, per Section 7.1.2.1
- Does not receive quarterly monitoring of serum phosphorus and iron indices (with documented Investigator review).

A listing of subjects with important protocol deviations will be provided.

#### 3.4.4. Analysis of Primary Endpoints

The primary endpoint is the time to composite endpoint of initiation of maintenance dialysis or all-cause mortality. A statistically significant hazard ratio less than 1 will be considered as confirmatory evidence of efficacy. The primary endpoint will be analyzed, based on the full analysis set, by Cox-proportional hazards regression model, with covariates included age, diabetes, atherosclerotic cardiovascular disease (ASCVD), congestive heart failure (CHF), and eGFR. The proportionality assumption of the model will be examined. HRs and corresponding 95% confidence intervals will be presented for the primary endpoint (initiation of maintenance dialysis or all-cause mortality). Analyses will be performed using the per protocol population as supportive.

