| Safety Assessments                                       |                        |               |                                  |                         |                         |                       |                                |
| Concomitant medication review j                      | X                      |               | X                                | X                       | X                       | X                     |                                |
| PRBC transfusions and/or dialysis access procedures             | X                      | ←————→        |                                  |                         |                         |                       |                                |
| Adverse Events of Special Interest n                 |                        |               | ←————→                           |                         |                         |                       |                                |
| SAE Assessment l                                     |                        |               | ←————→                           |                         |                         |                       |                                |
| Endpoint Assessment o                                |                        |               |                                  | X                       | X                       | X                     | X                              |
| Study intervention                                       |                        |               |                                  |                         |                         |                       |                                |
| Study drug prescription/provide study drug m         |                        | X             | X p                   | X                       | X                       |                       |                                |
| Study drug accountability q                          |                        |               |                                  |                         | X                       | X                     |                                |

| Study Period        |                        |               | Treatment Period b, c |                         |                         |                       | Follow-up d         |

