## 6.2 Exclusion Criteria

1. Patients who, in the opinion of the Investigator, have acute kidney injury rather than CKD.
2. Patients with planned/imminent maintenance dialysis, or that are anticipated to begin maintenance dialysis within 8 weeks from Screening, in the opinion of the Investigator.
3. A known allergy or intolerance to ferric citrate or any of its constituents.
4. Hypersensitivity reaction to previous oral iron therapy.
5. History of hemochromatosis or iron overload syndrome (e.g., hereditary sideroblastic anemia, thalassemia, polycythemia vera).
6. Active malignancy requiring current treatment except for non-melanoma skin cancer regardless of treatment.
7. Active drug or alcohol dependence or abuse (excluding tobacco use or use of medical or recreational marijuana) within the 12 months prior to Screening or evidence of such abuse, in the opinion of the Investigator.
8. Limited life expectancy ( $<6$  months) in the opinion of the Investigator.
9. Females who are known to be pregnant or are breast-feeding during Screening or are planning to become pregnant and breastfeeding during the study period.
10. Evidence of a clinically active infection requiring antibiotics at Randomization.
11. Unable to comply with study requirements or in the opinion of the Investigator, not clinically stable to participate in the study.
12. Use of an investigational medication or participation in an investigational study within 30 days prior to Day 1.
13. Patients with a scheduled date for receipt of living donor kidney transplant.

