### **9.2.1 Medical History and Demographics**

- Medical History and Demographics: Targeted medical history and demographic information will be collected. Targeted medical history will include an assessment of relevant medical history with particular emphasis on medical conditions that may lead to exclusion. Significant ongoing medical conditions or diseases should be documented.

Only the starting year of a condition will be required (e.g., not month or day). For conditions that may have multiple occurrences (e.g., myocardial infarction), only the year of the most recent event will be captured.

- Targeted relevant surgical history will be captured.
- The primary cause of CKD, current transplant status and current dialysis access (if applicable), will be collected.

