#### 3.1. Sample Size

The sample size for this study is driven by the primary endpoint, initiation of maintenance dialysis or all-cause mortality and is based on the observed data from the pilot study (Block, 2019) using nearly identical inclusion and exclusion criteria. The observed rate of the primary composite endpoint in the pilot study (all-cause mortality, maintenance dialysis or kidney transplant) for patients in the standard of care arm was 0.94 events per person-year of follow up. The observed hazard ratio was 0.42 (58% relative risk reduction,  $p=0.002$ ) for the primary composite endpoint when comparing ferric citrate treated patients versus usual care.

Assuming 1 year recruitment and 0.75 years of follow up (9 months) for each individual and a hazard ratio of 0.60 (40% relative risk reduction), a sample size of 400 patients (200 per arm) provides 90% power with a 2-sided alpha  $p < 0.05$ . Assuming a hazard ratio of 0.50 (50% relative risk reduction), a sample size of 225 patients provides 90% power with a 2-sided alpha  $p < 0.05$ .

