#### 3.4.5. Analysis of Secondary Endpoints

For the secondary endpoints listed below, Cox-proportional hazards model, using the same covariates as for the primary endpoint analysis, will be based on the full analysis set. Hazard ratios and corresponding 95% confidence intervals will be presented.

- Time to first event hospitalization reported as a SAE (excluding disease-related hospitalization [e.g., fistula replacement, dialysis initiation, kidney transplant] and elective procedures),
- Component of Primary – time to initiation of maintenance dialysis
- Component of Primary – time to all-cause mortality

Analyses will be performed using the per protocol population as supportive.

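### Baseline dialysis access, already collected at Screening, is not in the Cox models; if it is prognostic beyond eGFR, the plan gives up some power, by an amount the documents do not fix

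*SAP*

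**What the plan says.** SAP 3.4.4 analyses time to maintenance dialysis or death with a Cox model, "with covariates included age, diabetes, atherosclerotic cardiovascular disease (ASCVD), congestive heart failure (CHF), and eGFR". SAP 3.4.5 fits the three secondary endpoints "using the same covariates as for the primary endpoint analysis". One of these is time to maintenance dialysis alone.

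Protocol 9.2.1 states: "The primary cause of CKD, current transplant status and current dialysis access (if applicable), will be collected". The Schedule of Activities places medical history at Screening only. It also has a row for "PRBC transfusions and/or dialysis access procedures", marked at Screening and then through the study.

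The SAP's baseline table shell carries two of the three items in that Protocol 9.2.1 sentence, cause of CKD and transplant status, but not access. Access is not a subgroup factor in SAP 3.4.7 either. The SAP gives no reason for leaving it out.

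**The concern.** Dialysis is one of the two ways to reach the primary endpoint, and access is created in order to deliver it. A patient with access in place has been prepared for dialysis by a clinician who has seen the course of the disease. The eGFR used for eligibility and stratification is less informative about that course: one local value, up to 90 days old, from any common equation (Protocol 6.1, 7.3.1). Access could therefore carry prognostic information that the five listed covariates miss.

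If so, two things follow for the confirmatory analysis and for time to dialysis. A Cox model without a strong prognostic covariate estimates a hazard ratio closer to 1 and has less power than one that includes it. Also, randomisation is stratified by site and eGFR only, so the arms may differ in access by chance, and the model would not correct for it.

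**Working it through.** **Inputs from the documents (SAP 3.1).** Control rate: "for patients in the standard of care arm was 0.94 events per person-year of follow up". Design: "Assuming 1 year recruitment and 0.75 years of follow up (9 months) for each individual and a hazard ratio of 0.60". Target: "a sample size of 400 patients (200 per arm) provides 90% power with a 2-sided alpha" of 0.05. No dropout allowance is stated, so none is used.

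**1. Reproduce the planned size, unadjusted.**
- Control 9-month risk: 1 − exp(−0.94 × 0.75) = 0.506.
- Treated risk: 1 − exp(−0.94 × 0.60 × 0.75) = 0.345. The mean of the two is 0.425.
- Freedman events: (1.960 + 1.282)² × [(1 + 0.60)/(1 − 0.60)]² = 10.51 × 16 = 168.1, so 169. Then N = 169/0.4254, so 398, against the stated 400.
- Schoenfeld events: 4 × 10.51/(ln 0.60)² = 161.1, so 162. Then N = 381.
- With N = 400, 400 × 0.4254 = 170 events are expected. Power is 90.3% (Freedman) or 91.5% (Schoenfeld).

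The stated 90% therefore does not rely on adjusting for access.

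**2. Effect of leaving access out.** These inputs are assumed, because the documents give none of them: access prevalence 10-30%; access hazard ratio 1.5-4 given the other covariates; and one linear predictor L (SD 0.5) standing for the five SAP covariates. The hazard is λ₀ × exp(L + ln(access HR) × access + ln(0.60) × treatment). The log-odds of access rise with L, and λ₀ is set so that the control 9-month risk is 50.6%. There were 3,000 trials of 400 subjects per scenario. Each data set was fitted with treatment and L, without and with access.

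| Access HR | Prevalence | Treatment HR without access | Power without | Power with | Loss (points) |
|---|---|---|---|---|---|
| 1.0 | 20% | 0.599 | 91.7% | 91.5% | −0.2 |
| 1.5 | 10% | 0.599 | 91.8% | 91.7% | −0.1 |
| 1.5 | 20% | 0.599 | 91.5% | 91.7% | 0.1 |
| 1.5 | 30% | 0.603 | 91.4% | 91.8% | 0.4 |
| 2 | 10% | 0.605 | 90.0% | 91.5% | 1.5 |
| 2 | 20% | 0.606 | 90.4% | 92.0% | 1.6 |
| 2 | 30% | 0.608 | 90.2% | 91.8% | 1.6 |
| 3 | 10% | 0.616 | 88.5% | 91.3% | 2.9 |
| 3 | 20% | 0.624 | 86.9% | 91.7% | 4.8 |
| 3 | 30% | 0.625 | 86.2% | 91.8% | 5.6 |
| 4 | 10% | 0.623 | 87.3% | 91.9% | 4.5 |
| 4 | 20% | 0.640 | 82.6% | 91.1% | 8.5 |
| 4 | 30% | 0.644 | 81.7% | 92.1% | 10.4 |

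Losses were taken before rounding. With access in the model the mean treatment HR is 0.595-0.599 throughout. The simulation error of a single power figure near 90% is √(0.9 × 0.1/3000), about 0.5 points, so the rows for access HR 1.0 and 1.5 show no measurable loss.

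**3. Type I error.** With no treatment effect, prevalence 20% and access HR 3, the two-sided error is 5.3% without access and 5.1% with it.

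**4. Chance imbalance.** At an assumed 30% prevalence and 200 per arm, the 95% range of the between-arm difference is ±1.96 × √(2 × 0.3 × 0.7/200), about ±9 percentage points. At those edges, with a true HR of 0.60 and access HR 2, a model with treatment only gives about 0.57 or 0.65. Adding access returns about 0.60. The spread is wider at access HR 3.

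**The case against.** The strongest objection is that the loss rests on two inputs the documents do not supply. Neither document says how common access is, how strongly it predicts the endpoint, or that it marks the subjects nearest dialysis. At an access HR of 1.5 or below there is nothing to gain. This stands, and it is why the size can only be given as a range.

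Second, part of the information is already used or removed. eGFR is a covariate and a stratification factor, and Protocol 6.2 excludes "Patients with planned/imminent maintenance dialysis, or that are anticipated to begin maintenance dialysis within 8 weeks from Screening" in the investigator's opinion. This stands in part. The exclusion reaches 8 weeks while follow-up is 9 months, so a subject with access who is expected to start dialysis later remains eligible.

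Third, a reader might infer that the primary hazard ratio is biased, or that the trial is underpowered as planned. The documents do not support either reading. The shift is non-collapsibility: the two models estimate different hazard ratios, and randomisation protects both from systematic confounding. The test's error rate already allows for chance imbalance on average over randomisations. If 0.60 is read as the effect without access in the model, the planned power stands and adjustment would be an addition to it.

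Fourth, other collected variables, such as urine albumin, could be proposed in the same way, and age, ASCVD and CHF address the mortality component directly. Both remarks are fair. They bear on how much priority this deserves, but they do not count against adding access.

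Last, a reader might infer that access will go unreported. The shells are only a selection, and SAP 3.4.2 promises summaries of pretreatment variables, so its absence from the shell does not show that.

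**Conclusion.** The point holds as a missed efficiency gain of unknown size. Access is collected before randomisation, plausibly predicts dialysis start beyond eGFR, and is unused in the primary and secondary models. For an access HR of 2 to 4 and a prevalence of 10-30%, leaving it out moves a conditional HR of 0.60 to about 0.605-0.644 and costs about 1.5 to 10 power points. At 1.5 or below the cost is about nil. Any chance imbalance in access is also left unadjusted.

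The figures rest on the assumed prevalence, access HR and spread of the other covariates, on no dropout, and on the pilot's control rate. That rate includes kidney transplant, which the present primary endpoint does not. The primary analysis remains valid as written.

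**What to change.** Before unblinding, add to the covariate list in SAP 3.4.4 and 3.4.5: dialysis access in place, as recorded at Screening before randomisation (yes/no). Screening is the right anchor. Medical history is taken there, and the Schedule of Activities allows randomisation up to 8 days before Day 1, so a Day 1 definition could pick up access placed after randomisation. Because the item is collected only where applicable, state how a blank entry is coded. Add the same row to the baseline table shell.

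If access is left out on purpose, give the reason in SAP 3.4.4. Added after unblinding, the covariate would be post hoc.

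Cost: one degree of freedom per model, one line of SAP text and one table row. No new data are needed.

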#### 3.4.5. Analysis of Secondary Endpoints

For the secondary endpoints listed below, Cox-proportional hazards model, using the same covariates as for the primary endpoint analysis, will be based on the full analysis set. Hazard ratios and corresponding 95% confidence intervals will be presented.

- Time to first event hospitalization reported as a SAE (excluding disease-related hospitalization [e.g., fistula replacement, dialysis initiation, kidney transplant] and elective procedures),
- Component of Primary – time to initiation of maintenance dialysis
- Component of Primary – time to all-cause mortality

Analyses will be performed using the per protocol population as supportive.

#### 3.4.6. Tertiary Endpoint(s)

Tertiary endpoints include:

- Annualized rate of hospitalizations, incidence of hospitalizations, and proportion of days hospitalized prior to initiating maintenance dialysis
- Receipt of kidney transplant prior to experiencing a primary endpoint event
- Annualized incidence of receipt and cumulative dose of therapy for anemia including (individually, [ESA, intravenous iron, RBC transfusion]) prior to initiating maintenance dialysis
- Time to RBC transfusion

#### 3.4.7. Subgroup analyses

Data will be analyzed within the following subgroups of interest, as appropriate:

- eGFR within 3 months of Screening:
  - $\geq 15$  to  $\leq 20$  ml/min/1.73 m^2
  - $< 15$  ml/min/1.73 m^2
- Diabetes versus Non-diabetic patients
- 3-variable Kidney Failure Risk Equation (KFRE) score [Tangri 2011] within 3 months of Screening:

- ≥20% over 2 years
- <20% over 2 years
- Per protocol subsets using thresholds of 50%, 60%, and 80% of time on study that a subject received a non-zero dose of study medication.

### 3.5. Study attrition and disposition

We will summarize study attrition by treatment group, including patients randomized, received study drug, and completed. We will identify those who ended the study due to study endpoint (death, initiation of maintenance dialysis, transplant), adverse event, withdrawal of consent, lost to follow up, investigator decision, and all other reasons.

### 3.6. Safety Analyses

Hypotheses are not provided for safety outcomes. Observed measures of the following biochemical results will be reported at each visit and change from baseline at each visit: serum phosphorus, ferritin, TSAT, hemoglobin, and eGFR. Additionally, for hemoglobin and serum phosphorus, the proportion of patients within clinical standard of care range, using last on treatment value will be reported.

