### **3.2.2      Hyperphosphatemia**

In healthy individuals, phosphate is primarily eliminated by the kidneys, which effectively regulate phosphate balance and blood phosphate concentration. With decreasing kidney function, and other changes associated with CKD, there is a marked decrease in phosphorus excretion in the urine, leading to hyperphosphatemia. Hyperphosphatemia contributes to bone disease, vascular calcification, cardiovascular events, and mortality [Martin and Gonzalez 2011].

Restriction of dietary phosphate is usually not sufficient to control hyperphosphatemia in patients with DD-CKD; therefore, these patients are treated with orally administered phosphate binders which effectively bind dietary phosphate and facilitate fecal elimination rather than intestinal absorption. However, different phosphate binders differ in their safety profile, and all pose a high pill burden [Salusky 2006]. Specific safety or cost concerns with existing phosphate binders resulted in a persistent high level of unmet need for patients with hyperphosphatemia, which resulted in the development of ferric citrate as a phosphate binder in patients with DD-CKD.

Ferric citrate reduces intestinal phosphate absorption by precipitating phosphate in the intestine. The ferric iron from ferric citrate reacts with the phosphorus in the GI tract and precipitates as ferric phosphate or ferrous phosphate. The latter are insoluble and are excreted in the stool. Citrate is absorbed, potentially alleviating the metabolic acidosis that occurs in patients with

renal failure. Ferric citrate is approved for the control of serum phosphorus levels in adult patients with CKD on dialysis.

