### **3.3 Risk/Benefit Assessment**

#### **3.3.1 Known Potential Risks**

A thorough summary of the risks of ferric citrate is provided in the Investigator Brochure. (Edition 14, 10 March 2020). The main source of information on the safety of ferric citrate in humans comes from two main datasets. One dataset, the risks Pooled Safety Set – Hyperphosphatemia, is based on the integrated data from four completed studies (Studies 304, 305, PBB00101, and 201). These studies involved subjects with DD-CKD treated for hyperphosphatemia with ferric citrate for up to 1 year at dosages of up to 12 g/day. In these four studies, a total of 557 subjects received ferric citrate, 149 subjects received active control and 111 subjects received placebo.

The second dataset, the Pooled Safety Set – IDA, is based on the integrated data from 3 studies (Studies 306, 204, and 207). These studies involved 405 unique subjects (excluding 9 subjects treated in Study 204 and Study 306) with NDD-CKD IDA. In these 3 studies, 301 received ferric citrate (including 81 subjects treated with placebo in the Randomized Period and ferric citrate in the Extension Period of Study 306 and excluding 2 subjects treated with ferric citrate in Study 204 and Study 306) and 188 received placebo (excluding 1 subject treated with placebo in Study 204 and Study 306).

In the hyperphosphatemia pooled safety set, the incidence of subjects who experienced at least one treatment-emergent adverse event (TEAE) was lower in the all ferric citrate group (77.5%) compared with subjects on active control (89.3%). The most common TEAEs in subjects receiving ferric citrate were diarrhea (20.8%), discolored feces (19.4%), and nausea (11.1%). The most common TEAEs in subjects receiving active control were vomiting (14.8%), nausea (14.1%), diarrhea (14.1%), dyspnea (13.4%), vascular access complication (11.4%), hypotension (10.7%), and cough (10.1%).

In the IDA pooled safety set in the randomized periods, the incidence of subjects who experienced at least 1 TEAE was higher among subjects who received ferric citrate (75.3%) than among subjects who received placebo (61.7%). The most common TEAEs in subjects receiving ferric citrate were discolored feces (21.6%), diarrhea (20.5%), constipation (18.4%), nausea (9.5%), hyperkalemia (5.3%), and abdominal pain (4.7%). The most common TEAEs in subjects receiving placebo were diarrhea (12.2%), constipation (10.1%), and nausea (4.3%).

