## **8.0 DISCONTINUATION OF STUDY INTERVENTION AND PARTICIPANT DISCONTINUATION/WITHDRAWAL**

### **8.1 Discontinuation of Study Drug**

#### **8.1.1 Temporary Interruption of Study Drug**

Discontinuation from study drug is different from discontinuation from the study, and remaining study procedures will be completed as indicated by the study protocol. The Investigator is strongly encouraged to resume study drug as soon as the reason for temporary interruption is over. Reasons for temporary discontinuation of study drug include:

- Drug-related AEs per the Investigator's discretion
- Unforeseen circumstances per the Investigator's discretion
- Serum phosphorus <3.0 mg/dL
- TSAT is >50%
- Ferritin >500 ng/mL
- Repeated red blood cell transfusions (>4 units of red blood cells within any 6-month period of time). See Section 7.5.3.
- Significant elevation in liver enzymes (SGOT and/or SGPT) >3X ULN or pancreatic enzymes (amylase and/or lipase) >2X ULN or elevation in total bilirubin >2X ULN, without an identifiable alternate etiology. Study drug should not be resumed prior to discussion with Medical Monitor.

The study drug may be restarted when the reason for temporary discontinuation is resolved. If study drug is temporarily discontinued due to elevations in iron indices, both TSAT and ferritin laboratory values must be within protocol-defined ranges prior to resumption of study drug.

The data to be collected at the time of study drug discontinuation should be in accordance with the SoA.

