**Table 2 Typical Quarterly Laboratory Assessments**

| Hematology                  | Iron Indices  | Serum Chemistry  |
|-----------------------------|---|--|
| Complete Blood Count        | Ferritin*
TSAT*
Total iron
Total iron binding capacity | Phosphorus*
Calcium
Renal Panel (sodium, potassium, bicarbonate, chloride, BUN, creatinine, glucose)
Hepatic Panel (albumin, AST, ALT total bilirubin, ALP, total protein)
Magnesium
eGFR |
| Additional Laboratory Tests | Urine Tests   |  |
| PTH
Cystatin-C           | Urine albumin or protein; creatinine ratio                      |  |

ALP: alkaline phosphatase; AST: aspartate aminotransferase; ALT: alanine aminotransferase; BUN: blood urea nitrogen; eGFR: estimated glomerular filtration rate; PTH: parathyroid hormone; TSAT: transferrin saturation.

\*Assessment required at a frequency of no less than quarterly (90 days).

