#### **9.6.4    Reporting Adverse Events**

Non-serious AEs (with the exception of Adverse Events of Special Interest in Section 9.5.2) will not be collected in source documents or reported in the eCRF.

All SAEs will be collected in source documents and reported in the eCRF.

All Adverse Events of Special Interest will be collected in the source documents and reported in the eCRF.

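### SAP 3.6 leaves potassium out of its named safety laboratory analytes, although the protocol lists hyperkalemia as a common event on ferric citrate and non-serious events are not collected

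*SAP*

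**What the plan says.** SAP 3.6 lists what is reported at each visit and as change from baseline: "serum phosphorus, ferritin, TSAT, hemoglobin, and eGFR". For hemoglobin and phosphorus it adds the proportion of patients in the standard-of-care range at the last on-treatment value. No other analyte is named there, and the baseline table shell in SAP 5 has no potassium row.

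Protocol 3.3.1 gives the most common treatment-emergent events in the pooled iron-deficiency-anemia set, which is the non-dialysis CKD population. The ferric citrate list closes with "hyperkalemia (5.3%), and abdominal pain (4.7"%). The placebo list reads: "The most common TEAEs in subjects receiving placebo were diarrhea (12.2%), constipation (10.1%), and nausea (4.3"%). Hyperkalemia is not in the placebo list, and its placebo rate is not given anywhere.

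Protocol 9.6.4 says that non-serious events, other than the events of special interest, "will not be collected in source documents or reported in the eCRF". Protocol 9.5.2 and SAP 3.6.1 define two events of special interest, iron overload and hypophosphatemia.

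Potassium is in the typical quarterly panel of protocol Table 2: "Renal Panel (sodium, potassium, bicarbonate, chloride, BUN, creatinine, glucose"). Protocol 9.4 says the routine laboratory values in the Schedule of Activities go into the eCRF.

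**The concern.** A potassium abnormality that needs intervention meets the protocol's own definition of an adverse event (9.6.1.1). Unless it is also serious, it is not recorded as one. Protocol 9.4 does not ask investigators to judge the clinical significance of standard-of-care results other than phosphorus and iron indices, and protocol 11.9 rests safety oversight on the collection of SAEs. The potassium values themselves are therefore the only systematic source for comparing non-serious hyperkalemia between arms, and the section that says which laboratory values are reported does not name them.

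At stake is how much the trial can say about safety. Every subject enters with eGFR of 20 or below. The background data for the drug name hyperkalemia as common, and this trial has a placebo arm that could supply the missing comparison rate. Without a pre-specified summary, that comparison is either not made or is made with an analyte and cut-off chosen after the data are seen.

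**Working it through.** This is mainly a check of one part of the plan against another.

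| Analyte | Where the protocol brings it up | In protocol Table 2? | Named in SAP 3.6? |
|---|---|---|---|
| Phosphorus, TSAT, ferritin | Dose adjustment, 7.1.2.1 | Yes, marked as required | Yes |
| Potassium | Hyperkalemia 5.3%, 3.3.1 | Yes, not marked as required | No |
| AST, ALT, total bilirubin | Interruption criteria, 8.1.1 | Yes, not marked as required | No |
| Amylase, lipase | Interruption criteria, 8.1.1 | No, and not in the Schedule of Activities | No |

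**The plan's figure.** The counts behind 5.3% are not printed, so it cannot be reproduced directly. As a consistency check, of all denominators from 100 to 301, only 190 fits all seven ferric citrate percentages in that paragraph of 3.3.1; 10/190 = 5.3%.

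**Expected number.** Inputs: 5.3% (protocol 3.3.1) and 200 per arm (SAP 3.1). 200 × 0.053 = 10.6 ferric citrate subjects with a hyperkalemia event.

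**Share not recorded as an adverse event.** The documents do not give the serious share, so 5% to 30% is assumed.
- 5% serious: 10.6 × 0.05 = 0.5 recorded as SAEs; 10.6 × 0.95 = 10.1 not recorded.
- 30% serious: 10.6 × 0.30 = 3.2 recorded as SAEs; 10.6 × 0.70 = 7.4 not recorded.

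**Excess over placebo.** This cannot be computed. If both lists were cut at the same frequency, which the protocol does not say, the placebo rate would lie between 0 and 4.3%. The difference would then lie between 5.3 − 4.3 = 1.0 and 5.3 points, too wide a range to call a signal.

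**What a count could show.** With 200 per arm and 5.3% on ferric citrate, a two-sided 5% comparison has power of about 69% if the placebo rate is 1%, 42% if 2%, and 7% if 4.3% (assumed rates). A threshold count is therefore descriptive, and the by-visit potassium values should be shown beside it.

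**The case against.** The strongest reply is that the SAP already covers potassium in general terms. SAP 3 says collected data will be tabulated and listed. SAP 3.4.1 provides descriptive statistics and change from baseline, within and between groups, for laboratory parameters. SAP 3.6.1 includes laboratory values in its scope, and the shells are described as a selection. This stands in part. A reader might infer that potassium would appear nowhere in the output; the documents do not support that. What they lack is a named analyte, a by-visit summary and a threshold, and SAP 3.6 supplies names for five other analytes.

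Serious cases are captured. Hyperkalemia that leads to hospitalization, threatens life or is medically important is an SAE, doubtful cases are treated as SAEs (protocol 9.6.1.2), and SAEs are tabulated by preferred term and arm. The gap is confined to non-serious cases. Limiting adverse event collection is also a reasoned choice: protocol 9.5.2 cites an approved drug with an established profile and a labelled maximum twice the study's. That explains not collecting the events. It does not explain leaving values already in the eCRF out of the named list.

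A reader might also infer that ferric citrate raises potassium. With no placebo rate, no stated cut-off for the common-event lists, and no mention of hyperkalemia among the common events in the dialysis pooled set, that is not shown.

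A further tempting reading is that bicarbonate must be reported too, to explain any effect on dialysis start, because protocol 3.2.2 says "Citrate is absorbed, potentially alleviating the metabolic acidosis that occurs in patients with" renal failure. No objective or endpoint asks that question. By-visit means would not answer it either, since subjects who start dialysis leave the study.

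**Conclusion.** The point holds as a reporting gap that should be closed; it does not threaten the primary analysis. SAP 3.6 omits an analyte that the protocol's own safety background brings up, and restricted adverse event collection leaves no specified by-arm summary of non-serious hyperkalemia. The size is about 10.6 expected cases among 200 ferric citrate subjects, of which about 7.4 to 10.1 would not be recorded as adverse events.

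This assumes that the pooled 5.3% carries over to this population, dose and 9-month exposure, that 200 per arm are treated, and that 5% to 30% of cases are serious. Protocol 3.3.1 gives no dose for the pooled studies. Where protocol 3.3.2 states their length, the placebo-controlled periods were 12 and 16 weeks. No scaling to 9 months is attempted.

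A separate and minor matter is that protocol 8.1.1 includes "pancreatic enzymes (amylase and/or lipase) >2X ULN" among the reasons to interrupt study drug, while neither analyte is in Table 2 or the Schedule of Activities. A reader might infer that the criterion cannot operate. The documents do not support that, because values obtained in routine care could still meet it. It is a mismatch of wording for the sponsor to reconcile.

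**What to change.** In SAP 3.6:
- Add potassium to the observed and change-from-baseline summaries at each visit, by arm, with the number of subjects contributing at each visit.
- Add the number of subjects per arm with any post-baseline potassium above cut-offs that the sponsor fixes and records before unblinding.
- Optionally, count subjects per arm who cross the hepatic thresholds already written in protocol 8.1.1, using AST, ALT and total bilirubin values in the eCRF.

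In the protocol, reconcile section 8.1.1 with Table 2 and the Schedule of Activities on amylase and lipase. How to do so is for the sponsor.

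The cost is a few table rows and one clarification of wording, with no new visits or samples and no change to endpoints or sample size. The limitation is that these samples are taken as available under standard of care and potassium is not marked as required. Counts of subjects with any high value will therefore depend on how often each site tests, and by-visit means describe only subjects still in the study. Both belong in a table footnote, and the results should be read descriptively.
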